1.19. Definitions

Adverse Event (AE): any untoward medical occurrence in a patient or clinical study subject.

Serious Adverse Event (SAE): any untoward and unexpected medical occurrence or effect that:

- **Results in death**
- **Is life-threatening** – refers to an event in which the subject was at risk of death at the time of the event; it does not refer to an event which hypothetically might have caused death if it were more severe
- **Requires hospitalisation**
- **Results in persistent or significant disability or incapacity**
- **Is a congenital anomaly or birth defect**

Medical judgement should be exercised in deciding whether an AE is serious in other situations. Important AEs that are not immediately life-threatening or do not result in death or hospitalisation but may jeopardise the subject or may require intervention to prevent one of the other outcomes listed in the definition above, should also be considered serious.

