1.20. Expected adverse events

1.20.1. Potential adverse events related to RSV and influenza infection

We would expect subjects to experience typical symptoms of a common cold (including, but not limited to: fever, headache, malaise, rhinorrhoea, nasal congestion, sneezing, sore throat, and cough). These would not be deemed adverse events, unless in the opinion of the study doctor. However, fever greater than 38°C for more than three consecutive days or withdrawal from the study due to intolerable symptoms in more than two subjects in any arm will lead to a suspension of the study. The safety monitoring committee will be convened to determine any systematic cause for unexpectedly severe symptoms.

Any influenza-like illness resulting in

- **Sustained elevated heart rate >120bpm AND**
- **Sustained low blood pressure SBP<100**
- **Sustained elevated respiratory rate >30/min AND**
- **Sustained low blood oxygen SaO₂<94%**
- **Evidence of pneumonia on clinical examination**
- **New ECG abnormalities**

will lead to referral for assessment in Accident and Emergency. Hospitalisation of any subject will lead to immediate suspension of the trial. The safety monitoring committee will be convened to assess the clinical evidence in order to determine whether the study may proceed.

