1.21.2. Serious AEs

An SAE form should be completed and faxed to the Chief Investigator and the Sponsor within 24 hours. The safety monitoring committee (see Section 12) will also be informed and a meeting convened as soon as possible.

All SAEs should be reported to the West London REC 2 Research Ethics Committee where in the opinion of the Chief Investigator, the event was:

- 'related', i.e. resulted from the administration of any of the research procedures; and
- 'unexpected', i.e. an event that is not listed in the protocol as an expected occurrence

Reports of related and unexpected SAEs should be submitted to ethics, the sponsor and the R&D office within 15 days of the Chief Investigator becoming aware of the event, using the NRES SAE form for non-IMP studies.

Contact details for reporting SAEs

[contact] for the attention of [name] and/or [name]
Please send SAE forms to: [name]
[contact] (Mon to Fri 09.00 – 17.00)

ASSESSMENT AND FOLLOW-UP

Study participants will be seen frequently during the study period, and daily for 10 days following infection. They have details to contact the study doctor and research nurses and will be offered daily telephone contact. In this way, participants will be assessed regularly by the investigating team and any adverse events detected rapidly; subjects meeting the criteria for a serious adverse event will be offered prompt treatment as appropriate.

Subjects will have completed the study when they have had final convalescence investigations, expected to be 28 days after the initial inoculation with the influenza virus and 196 days after initial inoculation with the RSV virus. The overall study will be completed when sufficient numbers of subjects have been recruited. The end of the study is defined as the last visit of the last participant.

When the study is completed they will not be routinely followed-up. Subjects will return to the care of their GP following completion of the study.

STATISTICS AND DATA ANALYSIS

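### The SAE definition in section 1.19 makes unexpectedness a condition of seriousness, contradicting section 1.21.2 and leaving serious but expected events without a 24-hour reporting route

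*Combined protocol and SAP*

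**What the plan says.** Section 1.19 (Definitions) defines an adverse event without any reference to expectedness: "any untoward medical occurrence in a patient or clinical study subject". The definition of a serious event adds a condition: "any untoward and unexpected medical occurrence or effect that" meets one of five criteria, among them "Requires hospitalisation".

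Section 1.20 is headed as a list of expected adverse events. Within it, 1.20.1 says that typical cold symptoms are anticipated, gives an explicitly non-exhaustive list, and adds: "These would not be deemed adverse events, unless in the opinion of the study doctor". The same section states: "Hospitalisation of any subject will lead to immediate suspension of the trial". It then says that the safety monitoring committee will be convened to decide whether the study may go on.

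Section 1.21 asks for all adverse events to be reported and refers the reader to the procedures that follow it. Section 1.21.1 requires events to be recorded whether or not they were expected, but its heading limits it to non-serious AEs. Section 1.21.2 requires an SAE form to reach the Chief Investigator and Sponsor within 24 hours, and the committee to be informed and to meet as soon as possible. It sends SAEs to the ethics committee only if they are related and also unexpected, the latter meaning "an event that is not listed in the protocol as an expected occurrence".

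The Study Management section provides for a monthly committee meeting on all adverse events.

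**The concern.** Seriousness concerns the outcome of an event; expectedness concerns whether the protocol foresaw it. A reporting scheme normally uses the first to decide who must be told quickly within the study, and the second to decide what goes on to outside bodies. Section 1.19 folds the second into the first.

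At stake is prompt notice to the Sponsor. The participants are healthy volunteers deliberately infected with RSV or influenza, so some illness is foreseen by design and the question of what counts as expected will arise. If a serious event is judged expected, the literal definition takes it off the 24-hour route. The SAE definition is also relied on elsewhere: section 1.9 (Withdrawal criteria) points to the SAE section, and the Assessment and Follow-up section refers to subjects who meet SAE criteria.

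**Working it through.** No arithmetic applies: the documents give no SAE rate, no expected number of SAEs and no threshold based on an SAE count. The check is to set the sections side by side and follow each type of event through them. It assumes that *unexpected* in 1.19 has the meaning given in 1.21.2, the only definition the documents offer.

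**Step 1: are the two uses of unexpectedness compatible?** Under 1.19 every SAE is unexpected. Section 1.21.2 selects SAEs that are related and unexpected. Given 1.19, that selection equals the SAEs that are related, and the unexpectedness test removes nothing. The test has a function only if SAEs can be expected, which 1.19 rules out. The two sections contradict each other.

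**Step 2: which route does each type of event take?**

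- *Non-serious, expected or not:* recorded under 1.21.1 and discussed by the committee.
- *Meets a seriousness criterion, unexpected:* an SAE under 1.19. Section 1.21.2 then requires the 24-hour form and committee notice, plus the ethics report if related.
- *Meets a seriousness criterion, expected:* not an SAE under 1.19, so 1.21.2 is not triggered. It is not a non-serious AE in any ordinary sense, so 1.21.1 does not fit. What remains is the general instruction in 1.21, which refers back to these same two procedures, and the monthly meeting.

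**Step 3: can a serious event be judged expected?** It can, though not readily. The only things 1.20.1 says it anticipates are typical cold symptoms, but the list is open and includes fever and malaise. The referral criteria in 1.20.1 and the dislodged sampling strip in 1.20.2 also stand under the heading of expected adverse events. Two readers could classify the same event differently.

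**Step 4: what catches the third type of event?**

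- *With hospitalisation:* 1.20.1 suspends the trial and convenes the committee whatever the expectedness. It sets no time limit for notice and does not mention the Sponsor, so only the 24-hour form is missing.
- *Serious on another criterion, without hospitalisation* (for example life-threatening but resolved without admission): the hospitalisation rule does not apply.
- *The judgement clause in 1.19:* "Medical judgement should be exercised in deciding whether an AE is serious in other situations". It does not repeat the unexpectedness condition, but it is directed at events that fall short of the listed outcomes, so it does not restore an event that meets a listed criterion and fails only on expectedness.
- *General AE reporting:* it applies if the event counts as an AE. For listed symptoms, 1.20.1 leaves that to the study doctor.

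**The case against.** The strongest reply is that this is a drafting slip with little practical effect. The anticipated events are bounded by the word typical, and 1.20.1 itself treats prolonged fever or intolerable symptoms as unexpectedly severe. An illness bad enough for admission would therefore ordinarily be unlisted, hence unexpected, hence an SAE. Hospitalisation has its own rule. The study doctor may class expected symptoms as AEs, section 1.14 has all bronchoscopy events recorded and reported, participants are seen daily in confinement, and the committee reviews every AE monthly.

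Most of this stands, and it rules out two stronger readings. A reader might infer that a volunteer hospitalised with challenge illness would escape the safety committee; 1.20.1 says the opposite. A reader might also infer that the suspension rule fails because it depends on an SAE form; the documents tie suspension to hospitalisation itself.

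The reply does not remove the contradiction between 1.19 and 1.21.2. Nor does it supply a 24-hour route to the Sponsor for a serious event judged expected: a monthly meeting is no substitute, and the hospitalisation rule covers one seriousness criterion of five.

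**Conclusion.** The definition is wrong as written. Section 1.19 mixes seriousness with expectedness and contradicts 1.21.2. Followed literally, it leaves a serious event judged expected without the 24-hour form to the Chief Investigator and Sponsor, and 1.21.1 does not fill the gap. Such an event loses the SAE label and the form; it does not escape all reporting.

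A reader might infer that the SAE rate will be understated, and might illustrate this with the planned 16 per arm: one event left out turns 1/16 (6.25%) into 0/16. The documents do not support that as a finding. The Statistics and Data Analysis section plans no SAE rate, the 16 per arm was chosen for T-cell counts, and the illustration assumes both that a serious event occurs and that it is judged expected. Any undercount is zero if no serious event is judged expected, and grows by one for each that is. The documents give no basis for saying how many that would be.

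The conclusion rests on a literal reading of 1.19 and on the 1.21.2 meaning of *unexpected* applying there too.

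**What to change.** In 1.19, delete the words *and unexpected* from the SAE definition, so that seriousness alone triggers the 24-hour form and committee notice. In 1.21.2, keep relatedness and unexpectedness only as the filter for reports to the ethics committee.

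Then reconcile the neighbouring sections. Section 1.20 should say that listing an occurrence as expected does not take it out of SAE reporting once a seriousness criterion is met; otherwise the provision that listed symptoms are normally not AEs could reopen the gap. Section 1.21.1 should make clear that recording regardless of expectedness applies to serious events too. The suspension rule in 1.20.1 need not change for this purpose.

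The cost is two words deleted, a short reconciliation, and possibly a few more SAE forms. No analysis or sample size is affected.

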1.20. Expected adverse events

1.20.1. Potential adverse events related to RSV and influenza infection

We would expect subjects to experience typical symptoms of a common cold (including, but not limited to: fever, headache, malaise, rhinorrhoea, nasal congestion, sneezing, sore throat, and cough). These would not be deemed adverse events, unless in the opinion of the study doctor. However, fever greater than 38°C for more than three consecutive days or withdrawal from the study due to intolerable symptoms in more than two subjects in any arm will lead to a suspension of the study. The safety monitoring committee will be convened to determine any systematic cause for unexpectedly severe symptoms.

Any influenza-like illness resulting in

- **Sustained elevated heart rate >120bpm AND**
- **Sustained low blood pressure SBP<100**
- **Sustained elevated respiratory rate >30/min AND**
- **Sustained low blood oxygen SaO₂<94%**
- **Evidence of pneumonia on clinical examination**
- **New ECG abnormalities**

will lead to referral for assessment in Accident and Emergency. Hospitalisation of any subject will lead to immediate suspension of the trial. The safety monitoring committee will be convened to assess the clinical evidence in order to determine whether the study may proceed.

1.20.2. Potential adverse events of bronchosorption

Bronchosorption is likely to have less adverse effects than bronchoalveolar lavage, brushing and biopsy (the standard bronchoscopy tools) as it should not cause bleeding, infection or a reactive pyrexia. The only additional adverse event relating specifically to bronchosorption is dislodgement of the SAM from the forceps. If this does occur the SAM can be retrieved using standard endobronchial forceps and snares available routinely in the bronchoscopy suite. Emergency procedures SOP is in place.

1.20.3 Potential adverse effects of chest X-ray

Volunteers participating in this study will receive 1 chest Xray, which is entirely for research purposes. The estimated dose will be 0.02mSv (national Diagnostic Reference Level), which is approximately equivalent to 3 days natural background radiation and carries risk of inducing a cancer of approximately 1:1000,000 based on risk factors for a healthy adult. This is classified as a trivial risk level (ICRP 62).

1.21. Reporting procedures

All adverse events should be reported. Depending on the nature of the event the reporting procedures below should be followed. Any questions concerning adverse event reporting should be directed to the Chief Investigator in the first instance.

1.21.1. Non serious AEs

All such events, whether expected or not, should be recorded. These will be discussed by the safety monitoring committee (see Section 12)

1.21.2. Serious AEs

An SAE form should be completed and faxed to the Chief Investigator and the Sponsor within 24 hours. The safety monitoring committee (see Section 12) will also be informed and a meeting convened as soon as possible.

All SAEs should be reported to the West London REC 2 Research Ethics Committee where in the opinion of the Chief Investigator, the event was:

- 'related', i.e. resulted from the administration of any of the research procedures; and
- 'unexpected', i.e. an event that is not listed in the protocol as an expected occurrence

Reports of related and unexpected SAEs should be submitted to ethics, the sponsor and the R&D office within 15 days of the Chief Investigator becoming aware of the event, using the NRES SAE form for non-IMP studies.

Contact details for reporting SAEs

[contact] for the attention of [name] and/or [name]
Please send SAE forms to: [name]
[contact] (Mon to Fri 09.00 – 17.00)

ASSESSMENT AND FOLLOW-UP

Study participants will be seen frequently during the study period, and daily for 10 days following infection. They have details to contact the study doctor and research nurses and will be offered daily telephone contact. In this way, participants will be assessed regularly by the investigating team and any adverse events detected rapidly; subjects meeting the criteria for a serious adverse event will be offered prompt treatment as appropriate.

Subjects will have completed the study when they have had final convalescence investigations, expected to be 28 days after the initial inoculation with the influenza virus and 196 days after initial inoculation with the RSV virus. The overall study will be completed when sufficient numbers of subjects have been recruited. The end of the study is defined as the last visit of the last participant.

When the study is completed they will not be routinely followed-up. Subjects will return to the care of their GP following completion of the study.

STATISTICS AND DATA ANALYSIS

Based on pilot data from de Bree et al., we calculate that a sample size of 16 in each arm will be sufficient to find a difference of 1.4 between epitope-specific T cell counts in blood and lung, with 80% power using a 2-sided unpaired t-test with 5% significance level (where the variability in each group is 1.3). T cell numbers will be compared between RSV and influenza using an unpaired t-test (if normality of the T cell distribution, or its transformation, is satisfactory as assessed by histogram with q-qplot and Shapiro-Wilks test) or a Mann-Whitney test (if normality is not satisfactory). We will perform microarray analysis on each of 6 patients prior to inoculation and at 3 post-baseline timepoints. Our main analysis will identify differentially expressed genes between influenza and RSV at each post-baseline timepoint. The sample size, calculated using the size package from bioconductor which provides pilot data of gene expression variability from the U95 package, predicts that 6 individuals in each group will give us 80% power to detect a potential fold change of 3 in up to 67% of the genes with a Bonferroni multiple testing correction with a genome-wide 5% significance level.

Quantitative assessments of symptom scores, lung function, virus load, leukocyte numbers and inflammatory markers will be compared within subjects to determine differences between baseline and during infection. Intra-subject differences will be analysed using ANOVA and 2-tailed paired Student's t-tests or Wilcoxon signed rank test as appropriate. Correlations between inflammatory cell, illness severity, viral load and leukocyte counts will be examined using Spearman's rank correlations to investigate possible causal relationships.

Data and all appropriate documentation will be stored for a minimum of 10 years after the completion of the study, including the follow-up period according to Imperial College London policy.

REGULATORY ISSUES

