1.10.3. Follow-up period (outpatient, day 11 – day 196)

Participants will return to the ICRRU or ICRF on days 14 and 28 post infection for assessment and sampling, including bronchoscopy on day 28. During the 6 months after challenge, subjects will be asked to report all episodes of upper respiratory tract symptoms. If an episode of natural infection occurs, the subject will be asked to re-attend for blood and upper respiratory tract samples to be collected. After 6 months, subjects will be asked to return for further samples to be taken, including bronchoscopy if subject has been included for this. A second dose of RSV administered a week later in the RSV arm only. Further samples will be collected at the peak of the secondary response 7 days post-infection. We will not do every test on every visit as can be seen from Table 2. The total study period for each subject is 210 in the RSV arm and 42 in the influenza arm.

STUDY PROCEDURES

A variety of procedures are carried out during the study period. The frequency and timing of these procedures are shown in above. For the screening, and days -14, 14, 28 and 196 visits, procedures will take place in the procedures room on ICRRU or ICRF; for days 0 to 10 and 168 to 179 subjects in the RSV and influenza arms of the study will reside in the confinement facility and procedures will take place there (with the possible exception of virus inoculation and bronchoscopy).

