1.14. Bronchoscopy

Bronchoscopies will be performed in the endoscopy suite at St Mary's Hospital, or at Hammersmith hospital, in accordance with BTS guidelines. During the confinement period, private transport from the confinement facility to the endoscopy suite will be mandatory. Subjects will be instructed to wear face masks during this visit, and staff will use appropriate personal protective equipment (PPE).

- Subjects will sign a consent form prior to being screened for the study and will **sign a separate consent form for each bronchoscopy**. The procedure will be explained during the assessment stage and **subjects will be given written information specifically regarding bronchoscopies in addition to the Participant Information Sheet**
- Subjects will fast for four hours prior to the procedure
- Resuscitation equipment (for intubation, ECG monitoring and defibrillation) and necessary drugs (salbutamol, theophylline, adrenaline, hydrocortisone) will be available in the bronchoscopy room
- Premedication may be given including:
 - Nebulised salbutamol 2.5mg 10-15 minutes prior to bronchoscopy
 - Sedation – midazolam (2-10mg) or fentanyl (50-100µg) as necessary
 - Lignocaine – gel and solutions (1-4%) for topical anaesthesia. The total dose will not exceed 400mg
- Supplemental oxygen at a rate of 2Lmin⁻¹ is given via a nasal cannula and oxygen saturations and heart rate are monitored with a pulse oximeter continuously. Intravenous access will be mandatory in all cases
- The subject will be monitored during the bronchoscopy by adequately trained clinical staff, according to Research Bronchoscopy SOP (V3).
- The following samples are collected in this order: (i) Bronchosorption using Synthetic Absorptive Matrix (SAM) (ii) Bronchial Brushings (iii) Bronchial Biopsy (iv) Bronchoalveolar lavage (BAL)
- All adverse events – pain, bleeding, hypoxia etc will be recorded and reported according to Section 8 of this protocol
- Subjects will be observed for a minimum of 2 hours and nil by mouth until safe
- Transportation will be arranged as subjects should not drive on the day of the procedure
- All subjects will have a contact telephone number on discharge

1.14.1. Bronchosorption:

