‘Bronchosorption™ FX·i is a non-sterile, single-use device consisting of a synthetic absorptive matrix (SAM™) strip enclosed within a catheter for bronchial sampling. Bronchosorption™ FX·i is designed to operate through a flexible video bronchoscope with a maximum working length of 815mm. The SAM™ strip is 1.0mm wide, designed to work with a minimum instrument channel diameter of 2.0mm.’ Hunt Developments UK (Ltd).

- The device will be passed down the bronchoscope.
- The probe will be deployed for up to 120 seconds in segmental and larger bronchi to allow the SAM to absorb local epithelial lining fluid (ELF).
- The probe will then be resheathed and removed via the operating port of the bronchoscope.
- This will be repeated up to 4 times with a new device.
- The SAM will be transferred to polypropylene tubes for transport on ice to the laboratory and stored at -80 degrees C until analysis.

1.14.2. BronchoBronchial Biopsies:

Six bronchial biopsies will be taken from the segmental and sub-segmental bronchi of the right lower and middle lobe (RLL, ML). This is performed using *Keymed* 2mm biopsy channel cupped and fenestrated biopsy forceps [FB-19C-1 (1111065)]; four biopsies will be placed in 4% paraformaldehyde and stored in paraffin blocks and two placed immediately into RNeasy[®] (Qiagen) stabilisation solution and refrigerated for 24 hours prior to freezing at -80°C.

1.14.3. Bronchial Brushings:

Four bronchial brushings will be taken from the left lower lobe (LLL) sub-segmental bronchi with a standard cytology brush. The brush is washed in a tube containing RNA Cell Protect[®] (Qiagen) to preserve cells prior to freezing at -80°C. A new brush is used each time the brushes are washed and discarded.

1.14.4. Bronchoalveolar Lavage (BAL):

- BAL is performed by instillation of sterile physiological (0.9%) saline at room temperature into the left upper lobe (LUL) bronchus in 30ml aliquots to a total of 180-240ml
- Aiming for 80% volume recovery and aspirating after each instillation
- The BAL fluid is collected into a plastic chamber and transferred to polypropylene tubes for transport on ice to the laboratory
- BAL processing - Keep BAL collected at bronchoscopy on ice at all times

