1.18. Clinical symptom scores

A self-completed diary card of both upper and lower respiratory tract clinical symptoms will be made at baseline 14 days prior to inoculation (prior to nasal washing and / or bronchoscopy), on day 0, and daily for 14 days.

Additionally, the symptom diary will be completed daily for 7 days after the 1st bronchoscopy (i.e. day -14 to day -7). This is to allow the effect of bronchoscopy on symptoms to be measured and adjusted.

Individual symptom scores will be accumulated over the six-day period of maximal illness (days 2-7) after inoculation and the baseline recording (including any effect measured from the 1st bronchoscopy where appropriate) subtracted from the post inoculation recordings. Thus, for a patient who has a score of zero on day 0 prior to inoculation, the maximum cumulative score for the following six days is 144.

Upper Respiratory Tract Symptoms

A total 'upper respiratory clinical symptom score' will be derived using a four-point scale (0-3 for absent, mild, moderate and severe) for each of the following eight respiratory symptoms: sneezing, headache, malaise, fever/chills, nasal discharge, nasal obstruction, sore throat and cough according to established methods, giving a maximum clinical severity score of 24. This is an established method for studies of common cold illnesses⁴⁴. Symptoms will be recorded at the same time of day and before any procedures such as bronchoscopy or nasal lavage are performed.

An example is shown below:

Symptom	Day 1	Day 2	Day 3	Day 4	Day 5	Day 6	Day 7
Sneezing							
Headache							
Malaise							
Fever / chills							
Nasal discharge							
Nasal obstruction							
Sore throat							
Cough							
Total score							

0 = absent, 1 = mild, 2 = moderate, 3 = severe

Definition of a clinical cold

A clinical cold is diagnosed if **two or more** of the following are present:

- A cumulative clinical symptom score of 14 or greater over a 6 day period
- Nasal discharge is present on three or more days over the six-day period post viral inoculation
- A subjective impression of a cold developing. This latter criterion is used because there are a few subjects who have had a very strong subjective impression of a clinical cold but the cumulative clinical score does not reach the arbitrary cut-off level

System, Lower Respiratory Tract and Other Symptoms

A diary card of lower respiratory tract symptoms will be completed with a scoring system outlined below.

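### Influenza participants complete the study on the day of a bronchoscopy with six biopsies, and no safety contact is scheduled afterwards

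*Combined protocol and SAP*

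**What the plan says.** - **Completion.** The Assessment and Follow-up section (after section 1.21.2) places completion at the final convalescent tests, "expected to be 28 days after the initial inoculation with the influenza virus and 196 days after initial inoculation with the RSV virus". It adds: "When the study is completed they will not be routinely followed-up". Subjects then revert to their general practitioner.
- **Day-28 procedure.** Section 1.10.3: "Participants will return to the ICRRU or ICRF on days 14 and 28 post infection for assessment and sampling, including bronchoscopy on day 28". Table 2 marks the bronchoscopy row on day 28.
- **Content.** Section 1.14.2: "Six bronchial biopsies will be taken from the segmental and sub-segmental bronchi of the right lower and middle lobe". Sections 1.14.1, 1.14.3 and 1.14.4 add up to four bronchosorption samples, four brushings and a lavage of 180-240 mL.
- **Cover afterwards.** Section 1.14: "Subjects will be observed for a minimum of 2 hours and nil by mouth until safe". It also provides a telephone number at discharge and requires bronchoscopy adverse events to be recorded.
- **Recognised effects.** Section 1.20.2 contrasts bronchosorption with lavage, brushing and biopsy, "as it should not cause bleeding, infection or a reactive pyrexia". The contrast implies that these effects belong to the standard tools.
- **Diary.** Section 1.18: "the symptom diary will be completed daily for 7 days after the 1st bronchoscopy". The other diary period after the first inoculation ends on day 14.
- **Study period.** Section 1.10.3 gives totals of 210 (RSV) and 42 (influenza), with no unit printed.

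**The concern.** The influenza arm's last study day is also the day of an invasive research procedure in healthy volunteers. Infection or fever need not show within 2 hours, and bleeding may also be noticed later. Someone who develops one of these the next day has already completed, has no study appointment and is under general practice care. The team learns of it only if the participant makes contact.

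Several safeguards depend on such events reaching the team. Section 1.19 makes hospitalisation a serious adverse event, section 1.20.1 suspends the trial if any subject is hospitalised, and the safety monitoring committee is to review all adverse events monthly. None of these works for an event that nobody reports.

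**Working it through.** Only day arithmetic is needed. Days are counted from inoculation.

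**1. Reproduce the stated study periods.** Period = completion day minus first study day (baseline visit, day -14, section 1.10.1).
- Influenza: 28 - (-14) = 42, as stated.
- RSV: 196 - (-14) = 210, as stated.

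Both match if the unit is days, so day 28 really is the end of the influenza arm.

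**2. Scheduled time after the last bronchoscopy.** Completion day minus day of the last bronchoscopy marked in Table 2.
- Influenza: 28 - 28 = 0 days.
- RSV: 196 - 182 = 14 days.

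**3. Scheduled contact after each bronchoscopy** (Tables 1 and 2, sections 1.16 and 1.18).

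| Bronchoscopy | Arm | What follows |
|---|---|---|
| Day -14 | Both | 7-day diary; examination on day 0 |
| Day 10 (section 1.10.2 allows day 7 or 10) | Both | Diary to day 14; visits with examination on days 14 and 28, that is 4 and 18 days later |
| Day 28 | Influenza | Nothing scheduled |
| Day 28 | RSV | Next visit day 161, 161 - 28 = 133 days later; no diary |
| Day 182 | RSV | Visit on day 196, 14 days later |

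**4. Look for a collection window.** Section 1.14 and sections 1.19 to 1.21.2 ask for adverse events to be recorded and reported. None gives an end date, and none says that collection continues after completion.

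**5. Test the readings that could change the result.**
- Section 1.10.3 does not expressly limit the six-month return visit to the RSV arm; only the second inoculation is so limited. Applied to influenza, this would contradict the day-28 completion and the total of 42, and the next visit would still be 133 days away.
- Section 1.10.3 also asks for reports of respiratory symptoms over six months without naming an arm. It covers upper respiratory symptoms only, not effects of bronchoscopy.
- Section 1.10.3 appears to place a six-month bronchoscopy about a week before the second inoculation, which Table 2 does not mark. If that were the last RSV procedure, the 14 days would lengthen and the contrast would widen.

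**The case against.** The strongest reply is that nothing excludes a late event. Section 1.21 asks for every adverse event to be reported, section 1.21.1 for every non-serious one to be recorded, and section 1.14 for bronchoscopy events to be recorded, all without an end date. Participants hold contact details, and the Assessment and Follow-up section offers daily telephone contact. Section 1.14 also relies on guidelines, an operating procedure and written bronchoscopy information that are not in the document and may contain aftercare arrangements.

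Much of this stands. A reader might infer that complications after day 28 fall outside the plan's safety collection altogether; the missing end date means that they do not. What remains is that no contact is scheduled. The offer of daily calls is not stated to run past completion, and a discharge number is a passive route.

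Other stronger inferences also fail:
- The 7-day diary might be read as a safety window that the plan forgot to repeat. Section 1.18 gives its purpose as measuring and adjusting for bronchoscopy's effect on symptom scores, and its items do not include bleeding.
- The day-10 bronchoscopy might seem to have the same gap. It does not: visits with examination follow on days 14 and 28.
- One might multiply 16 per arm by two arms and six biopsies to count unfollowed procedures. Section 1.10.3 suggests, for the six-month visit, that not everyone has bronchoscopy, so any such count is an assumption.

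**Conclusion.** The point holds as a gap in scheduled safety follow-up. Influenza participants who have the day-28 bronchoscopy complete that day with 0 scheduled days afterwards, against 14 days after the last RSV bronchoscopy in Table 2. The RSV arm has a weaker form of the gap: no visit for 133 days after its own day-28 procedure, but those participants are still in the study.

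This rests on reading the totals of 42 and 210 as days, on the Table 2 column positions for days 28 and 182, and on the daily telephone offer ending with the study period. It applies only to participants who have the procedure.

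A reader might go further and infer a falsely low complication rate, biased between arms. The documents do not support that. The statistics section plans no comparison of bronchoscopy complications, no frequency or timing of late effects is given, and neither arm has a diary after day 28. The supportable statement is that late events may be under-reported, by an unknown amount. The primary T-cell comparison is unaffected. The change is still worth making because it is cheap and concerns the safety of healthy volunteers.

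**What to change.** Reconcile section 1.10.3, section 1.14 and the Assessment and Follow-up section so that:
- adverse event and serious adverse event collection has a stated end, later than the day-28 bronchoscopy;
- completion in the influenza arm moves to that end and is closed by one scheduled telephone safety contact;
- the call asks about delayed effects of bronchoscopy and names bleeding explicitly, since the diary does not;
- RSV participants receive the same call after their day-28 bronchoscopy;
- the influenza total of 42 is updated to match, with its unit.

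The sponsor should set the length of the window. The 7-day diary after the first bronchoscopy and the 14 days after the last RSV bronchoscopy are reference points within the plan; neither fixes a particular completion day. The cost is one call per participant who has the procedure, a slightly longer influenza study period and a few lines of text, with no extra visit.
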